**Table 7.b Visit Analysis Windows for Part 2**

Visit	Scheduled Visit Day	Visit Window (Days)				
		Vital Signs, CCI, PK, C, Plasma Sample for AED, Concomitant Medications	CCI	ECG, Clinical Laboratory Tests	CCI, Serum/urine Pregnancy Test	Physical Exam, Neurological Exam
Baseline II		≤First Dose in Part 2	≤First Dose in Part 2	≤First Dose in Part 2	≤First Dose in Part 2	≤First Dose in Part 2
Visit 6	41	Day after First Dose in Part 2-53	Day after First Dose in Part 2-53			
Visit 7	85	54-Last Dose+7	54-Last Dose+7	Day after First Dose in Part 2-Last Dose+7	Day after First Dose in Part 2-Last Dose+7	Day after First Dose in Part 2-Last Dose+7

Note: Any value collected after the administration of first dose in Part 2 will be grouped under day after first dose in Part 2, except for PK, CCI and plasma sample for AED.

### 7.1.3 Conventions for Missing Adverse Event Dates

Adverse events with completely or partially missing dates will be imputed as follows.

#### 7.1.3.1 Imputation of missing or partial dates of AE start dates

- Month/year available and day missing:
  - If the month and year are the same as those in the first dose date in Part 1 and the event is not indicated as a pre-treatment event, the first dose date in Part 1 is to be used to impute the start date.
  - If the month and year are the same as those in the first dose date in Part 1 and the event is indicated as a pre-treatment event, the date prior to the first dose date in Part 1 is to be used to impute the AE start date. If the date prior to the first dose date in Part 1 is in previous month/year, set the start month/year to the previous month/year.
  - If the month and year are after the first dose date in Part 1 and the same as or before the last dose date in Part 1 plus 30 days for patients who do not continue to Part 2 or before the first dose date in Part 2, the first day of the month will be used for the start date.
  - If the month and year are the same as the first dose date in Part 2 and the same as the last dose date in Part 1, the first day of the month will be used for the start date.
  - If the month and year are the same as the first dose date in Part 2 and after the last dose date in Part 1, then the event is considered as a treatment emergent for Part 2 and the first dose date in Part 2 is to be used to impute the start date.

- If the month and year are after the first dose date in Part 2, the first day of the month will be used for the start date.
- Year available and month/day missing:
  - If the year is the same as the year of the first dose in Part 1 and same as or before the first dose in Part 2 and the event is not indicated as a pre-treatment event, the first dose date in Part 1 is to be used to impute the AE start date.
  - If the year is the same as the year of the first dose date in Part 1 and same as or before the first dose in Part 2 and the event is indicated as a pre-treatment event, the date prior to the first dose date in Part 1 is to be used to impute the AE start date. If the date prior to the first dose date in Part 1 is in previous month/year, set the start month/year to the previous month/year.
  - If the year is the same as the first dose date in Part 2 and after the last dose date in Part 1, the first dose date in Part 2 is to be used to impute the AE start date.
  - If the year is not the same as the year of the first dose date in Part 1 or the year of first dose date in Part 2, set the start date as January 1.
- Year/month/day all missing:
  - If the event is not indicated as a pre-treatment event, the first dose date in Part 1 is to be used to impute the AE start date.
  - If the event is indicated as a pre-treatment event, the date prior to the first dose date in Part 1 is to be used to impute the AE start date.

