## 10.2 Procedures

### 10.2.1 Collection and Reporting of AEs

#### 10.2.1.1 AE Collection Period

Collection of AEs will commence from the time informed consent is provided at Screening (Visit 1) and continue until screen failure or until the Follow-up Visit (Visit 9). For subjects who discontinue prior to study drug administration, AEs are collected until the subject discontinues study participation.

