#### 10.2.1.2 AE Reporting

At each study visit, the investigator will assess whether any subjective AEs have occurred. A neutral question, such as “How have you been feeling since your last visit?” may be asked. Subjects may report AEs occurring at any other time during the study.

All subjects experiencing AEs, whether considered associated with the use of the study drug or not, must be monitored until the symptoms subside and any clinically relevant changes in laboratory values have returned to Baseline or until there is a satisfactory explanation for the changes observed. All AEs will be documented in the AE page of the eCRF, whether or not the investigator concludes that the event is related to the drug treatment. The following information will be documented for each event:

1. Event term.
2. Start and stop date and time.
3. Frequency.
4. Intensity.
5. Investigator’s opinion of the causal relationship between the event and administration of study drug (related or not related).
6. Investigator’s opinion of the causal relationship to study procedure(s), including the details of the suspected procedure.
7. Action concerning study drug.
8. Outcome of event.

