### 7.11.1 **Adverse Events**

A Pre-Treatment Event (PTE) is defined as any untoward medical occurrence in a clinical investigation subject who has signed informed consent to participate in a study, but prior to administration of any study medication; it does not necessarily have to have a causal relationship with study participation.

An AE is defined as any untoward medical occurrence in a clinical investigation subject administered a drug; it does not necessarily have to have a causal relationship with this treatment. PTE and AE verbatim terms will be coded by SOC and PT using MedDRA (version 19 or later).

TEAEs for Part 1 will be defined as any sign, symptom, syndrome, or new illness, regardless of relationship to study drug, that occur after the first dose of study drug received in Part 1 and up to 30 days (onset date – last date of dose + 1 ≤ 30) after the last dose of study drug in Part 1 or

early termination. AEs that occur on the same day as the first dose of study drug in Part 1 but with missing time will be considered as TEAEs for Part 1.

TEAEs for Part 2 will be defined as any sign, symptom, syndrome, or new illness, regardless of relationship to study drug, that occur after the first dose of study drug received in Part 2 and up to 30 days (onset date – last date of dose + 1 ≤ 30) after the last dose of study drug in Part 2 or early termination. AEs that occur on the same day as the first dose of study drug in Part 2 but with missing time will be considered as TEAEs for Part 2.

TEAEs for Part 1 and 2 combined will be defined as any sign, symptom, syndrome, or new illness, regardless of relationship to study drug, that occur after the first dose of study drug received in Part 1 and up to 30 days (onset date – last date of dose + 1 ≤ 30) after the last dose of study drug in Part 2 or early termination. AEs that occur on the same day as the first dose of study drug in Part 1 but with missing time will be considered as TEAEs for Part 1 and 2.

TEAEs will be presented by severity (mild, moderate, and severe). Serious TEAEs, TEAEs leading to study drug discontinuation, and TEAEs leading to death will also be summarized using SOC and PT.

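### SAP 7.1.3.1 imputes incomplete AE start dates without using the recorded stop date, so an event that ended before the first dose and is not indicated as pre-treatment becomes a Part 1 TEAE

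*SAP*

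**What the plan says.** SAP 7.1.3.1 sets the start date in three situations that turn on the first dose in Part 1.

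- Day missing, month and year equal to those of the first dose: if "the event is not indicated as a pre-treatment event, the first dose date in Part 1 is to be used to impute the start".
- Month and day missing, year equal to that of the first dose: the same result for an event not indicated as pre-treatment.
- Whole date missing: "If the event is not indicated as a pre-treatment event, the first dose date in Part 1 is to be used".

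The counterpart for indicated events is that if "the event is indicated as a pre-treatment event, the date prior to the first dose date in Part 1 is to be used".

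SAP 7.11.1 then settles treatment emergence on the first-dose day: "AEs that occur on the same day as the first dose of study drug in Part 1 but with missing time" are Part 1 TEAEs. The same section defines a pre-treatment event as one arising after consent and before any study medication.

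SAP 7.1.3.2 holds the only check of one date against the other. When an end date has been imputed with the day missing or the whole date missing, and it falls before the start, the end is set equal to the start.

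On collection, Protocol 10.2.1.1 gathers adverse events from consent at Screening, which precedes dosing by 4 to 6 weeks. Protocol 10.2.1.2 introduces its list of items with "The following information will be documented for each event". The list includes start and stop date and time. It does not include a pre-treatment indicator.

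**The concern.** Placing an undated event on treatment is a sensible cautious convention when the record cannot say whether the event began before or after dosing. It is not sensible when the record already answers the question. An event whose recorded stop precedes the first dose cannot have begun on or after it, and on the SAP's own definition it is a pre-treatment event. The start-date rule ignores that evidence.

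Two things are at stake. The primary endpoint is the percentage of subjects with at least one TEAE, and it can gain an event that the data show to be pre-treatment; this error runs only towards more TEAEs. The analysis data can also hold events that start after they stop or, worse, have an informative partial stop date replaced.

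**Working it through.** The plan gives no figure to reproduce: there is no formal sample size calculation and TEAEs are summarised descriptively. The check is to run the written rules on an illustrative record.

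**Inputs.** First dose 16 April 2018 and recorded stop 10 April 2018 (both invented). Start rules from SAP 7.1.3.1, end rules from 7.1.3.2, TEAE rule from 7.11.1. Planned group sizes of 16 and 4 from SAP 4.4.

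**Step 1: rules as written.**

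| Start date | Recorded stop | Indicated as pre-treatment? | Imputed start | Analysis stop | Start after stop? | Part 1 TEAE? |
|---|---|---|---|---|---|---|
| Day missing (April 2018) | 10 April | No | 16 April | 10 April | Yes, 6 days | Yes |
| Month and day missing (2018) | 10 April | No | 16 April | 10 April | Yes, 6 days | Yes |
| All missing | 10 April | No | 16 April | 10 April | Yes, 6 days | Yes |
| Any of these three | 10 April | Yes | 15 April | 10 April | Yes, 5 days | No |
| All missing | March 2018 | No | 16 April | 16 April | No | Yes |
| All missing | March 2018 | Yes | 15 April | 15 April | No | No |

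In the last two rows the end is first imputed as 31 March. It is then moved forward to the imputed start, because it would otherwise precede it. The evidence that the event ended in March is overwritten, and a later check for start after stop would find nothing.

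**Step 2: effect on the primary percentage.** One subject whose only event in the part is misclassified changes the result by 100/n:

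- TAK-935: 100/16 = 6.25 points
- placebo: 100/4 = 25 points
- overall: 100/20 = 5 points

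A subject with another TEAE in that part contributes no change.

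**Step 3: reach of the day-missing branch.** It applies only when the start month is the month of first dose. Assume first doses spread evenly over a 365-day year. The days of that month before the first dose then average (7×465 + 4×435 + 378)/365 = 5373/365 = 14.7. Against a 42-day screening period this is 14.7/42 = 35%. Against 28 days, with the overlap capped at 28, it is 52%. These are shares of screening days on which a day-missing start would meet the rule. They are not probabilities of misclassification. The other two branches do not depend on the month.

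**Step 4: rules with a stop-date cap.** For the unindicated event with stop 10 April, the start becomes the earlier of the rule date and 10 April, which is 10 April. It precedes 16 April, so the event is not a TEAE. For the March stop, the latest compatible date is 31 March, so the start is 31 March. The imputed end of 31 March is no longer before the start and stands.

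**The case against.** The strongest reply is that the rule has a safeguard. It separates events by whether they are indicated as pre-treatment, and an indicated event never becomes a TEAE. SAP 7.11.1 also plans a table and a listing of pre-treatment events, so these must be identified anyway, and nothing in the SAP excludes deriving the indication from the stop date. This stands as a limit: only events without the indication can reach the primary endpoint. It does not remove the point, because the SAP does not say that the indication is so derived and the date inconsistency arises with or without it.

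A reader might infer that the indication cannot be trusted, because Protocol 10.2.1.2 does not list it and Protocol 10.1.1 calls every event from consent an adverse event. The documents do not support that. The list is not presented as a case report form specification, and the form itself is not among the documents. SAP 7.1.3.2 likewise relies on an ongoing indication that the list does not name, and SAP 7.11.1 separates pre-treatment events from adverse events for analysis. What can be said is that the source of the indication is not shown.

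Data controls also count. Protocol 12.1 provides for logic checks on inconsistent and missing dates, with queries to the site, and Protocol 13.1 provides for a blinded data review before lock. These should reduce the number of such records. They are described for the study database rather than for dates created by imputation, so they do not correct the rule.

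Finally, the 25-point figure concerns one placebo subject, whereas the primary endpoint is worded for events after TAK-935 treatment. It is fair to show it as the effect on the comparator column that SAP 7.11 presents, but not as the typical size of the problem.

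**Conclusion.** The point holds as a defect in a stated rule, of minor consequence. Under SAP 7.1.3.1 an event with an incomplete start that meets one of the three situations above, a recorded stop before the first dose and no pre-treatment indication is given a start at the first dose and counted as a Part 1 TEAE. An indicated event escapes that count but may still start after its stop. SAP 7.1.3.2 can erase a partial pre-dose stop.

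The size per affected subject is 6.25 points on TAK-935 or 25 points on placebo at the planned group sizes, and only where the subject has no other TEAE in that part. The documents give no frequency of incomplete dates. Taking 0 to 2 such records among 20 subjects is an assumption; at two subjects, both on TAK-935 and each with no other TEAE, the shift would be 2/16 = 12.5 points. A reader might go further and conclude that the primary result will be inflated. That does not follow, because every one of these conditions must coincide. The analysis is descriptive, so no error rate, power or test is touched.

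**What to change.** Add to SAP 7.1.3.1, ahead of the other rules and applied before 7.1.3.2:

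*If the recorded stop date, or the latest date compatible with a partial stop date, is before the first dose in Part 1, the event is treated as pre-treatment whatever its indication. In all Part 1 and Part 2 branches the imputed start date is the earlier of the date given by the rule and the recorded stop date (or the latest date compatible with a partial stop date).*

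This names a date that can be programmed and does not depend on how the pre-treatment indication is obtained. Taking the latest compatible date keeps the cautious convention where it belongs: a stop known only to the month of first dose does not prove that the event ended before dosing, so the event is still assigned to treatment unless it is indicated otherwise. Applying the rule before 7.1.3.2 prevents the end date from being pulled forward over a pre-dose stop.

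The cost is one rule in the SAP and one programming check that no imputed start is later than its recorded stop. It uses data already collected and changes no study procedure.

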Part 2 is an open-label continuation part consisting of 4 periods: a titration period (10 days), maintenance period (44 days), de-escalation period (3-6 days) and follow-up period (30 days).

Part 1 of the study is designed to investigate the safety, tolerability, PK, and PD in adult subjects with developmental and/or epileptic encephalopathies in a double-blind manner. CCI [REDACTED] will be investigated in an exploratory manner. Approximately 20 adult subjects who CCI [REDACTED]

[REDACTED] during the 4-week Baseline Period will be randomly assigned on Day 1 (Visit 2) to receive TAK-935 (n=16) or matching placebo (n=4) twice daily (BID) orally or via stable gastrostomy tube (G-tube)/ percutaneous endoscopic gastrostomy (PEG) tube for 30 days during the Double-Blind Treatment Period. Subjects will initiate IP (investigational product; TAK-935 or placebo) at 100 mg BID from Days 1 through 10. Subjects who cannot tolerate the 100 mg BID dosing will be withdrawn from the study. On Day 11 (Visit 3), subjects will return to the clinic and the IP dose will be increased to 200 mg BID; this dose level will be maintained from Days 11 through 20 but may be reduced to 100 mg BID in subjects who cannot tolerate the 200 mg BID dose or demonstrate safety concerns, based on the investigator's judgment and in consultation with the subject's caregiver, when applicable. On Day 21 (Visit 4), subjects will return to the clinic; at this visit, the investigator will review the subject's safety data and will discuss the benefit-risk with the subject or subject's legally acceptable representative before proceeding to increase the dose from 200 mg BID to 300 mg BID, and this dose level will be maintained from Days 21 through 30. The dose may be reduced to 200 mg BID in subjects who cannot tolerate the 300 mg BID dose or demonstrate safety concerns, as described above. Subjects for whom the dose was reduced to a lower dose level will stay on that dose level until the end of the Double-Blind Treatment Period. Three days after each dose up-titration or de-escalation, subjects will be contacted by phone to monitor study drug compliance, concomitant medication use, and AEs. Any change in dose will be documented in the subject's clinic chart and the subject's caregiver will be advised to note the same in the dosing card.

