Part 2 of the study is designed to investigate the safety, tolerability, PK, and PD of TAK-935 in adult subjects with developmental and/or epileptic encephalopathies in an open-label manner. All subjects who complete the Double-Blind Treatment Period in Part 1 will have the option to continue directly into the Open-Label Treatment Period in Part 2. Because some subjects may enter Part 2 after receiving placebo and others TAK-935 up to 300 mg BID and to maintain the study blind, all subjects will start on TAK-935 200 mg BID at the start of Part 2. On Day 31 (Visit 5), subjects will return to the clinic and receive TAK-935 200 mg BID from Days 31 to 40 but may be reduced to 100 mg BID in subjects who cannot tolerate the 200 mg BID dose or demonstrate safety concerns, based on the investigator's judgment and in consultation with the subject's caregiver, when applicable. Subjects who cannot tolerate the 100 mg BID dose or demonstrate safety concerns, based on the investigator's judgment and in consultation with the subject's caregiver, will be discontinued from the study. On Day 41 (Visit 6), subjects will return to the clinic; at this visit, the investigator will review the subject's safety data and will discuss the benefit-risk with the subject or subject's legally acceptable representative before proceeding to increase the dose from 200 mg BID to 300 mg BID, and this dose level will be maintained until the Final Visit (Visit 7) for the dose de-escalation phase. Subjects' dose may be increased or decreased before Day 41 (Visit 6) based on clinical condition (ie, increasing seizures) and investigator judgment. This dose may be reduced to 200 mg BID in subjects who cannot tolerate the 300 mg BID dose or demonstrate safety concerns, as described above. Subjects for whom the dose was reduced to a lower dose level will stay on that dose level until the Final Visit (Visit 7) for the dose de-escalation phase. Three days after each dose up-titration or de-escalation, subjects will be contacted by phone to monitor study drug compliance, concomitant medication use, and AEs. Any change in dose will be documented in the subject's clinic chart and the subject's caregiver will be advised to note the same in the dosing card.

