## 5.0 ANALYSIS ENDPOINTS

### 5.1 Primary Endpoint

Percentage of subjects with at least 1 treatment-emergent adverse event (TEAE), as reported by the subjects or subjects' caregivers or observed by the investigator, after TAK-935 treatment.

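### For subjects who enter Part 2, the AE start-date imputation moves incompletely dated events to before the first Part 2 dose, so possible open-label TAK-935 events drop out of the Part 2 primary endpoint

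*SAP*

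**What the plan says.** Part 1 treats subjects "for 30 days during the Double-Blind Treatment Period", randomised "to receive TAK-935 (n=16) or matching placebo (n=4) twice daily (BID) orally". Part 2 follows without a gap: "On Day 31 (Visit 5), subjects will return to the clinic and receive TAK-935 200 mg BID from Days 31 to 40" (SAP 4.4).

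SAP 7.1.3.1 sets the start-date rules:

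- **Day missing, transition month shared.** If the recorded month is that of the first Part 2 dose and is "the same as the last dose date in Part 1, the first day of the month will be used for the start date", the 1st is imputed.
- **Day missing, transition month not shared.** If the recorded month is that of the first Part 2 dose but later than that of the last Part 1 dose, "then the event is considered as a treatment emergent for Part 2 and the first dose date in Part 2 is to be used".
- **Year only, in the year of the first Part 1 dose, or date wholly missing, and not flagged pre-treatment.** Here "the first dose date in Part 1 is to be used to impute the AE start date".

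SAP 7.11.1 requires a Part 2 TEAE to start after the first Part 2 dose; onset on that same day with no time recorded also counts. A Part 1 TEAE may start up to 30 days after the last Part 1 dose (onset minus last dose plus 1, at most 30). That window is not shortened for subjects who go on to Part 2.

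The primary endpoint is the share of subjects with a TEAE reported or "observed by the investigator, after TAK-935 treatment" (SAP 5.1). Protocol 13.1.3.1 makes it a primary endpoint in each part.

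**The concern.** For a subject who continues, an incompletely dated AE could have begun on either side of the Part 2 boundary. The rules nearly always settle that doubt by choosing a date before the first Part 2 dose. They do not look at the stop date or the visit of report, and no sensitivity analysis is planned. The Part 2 TEAE percentage can therefore come out too low, and Part 2 is the longer exposure, with every subject on active drug.

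SAP 7.11.1 treats other missing AE attributes the opposite way: missing severity is tabulated as severe and missing relationship as related. Here missing information removes an event from the Part 2 table.

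**Working it through.** The plan gives no figure on this point to reproduce. The check applies the start-date rules and TEAE definitions to each possible first-dose date.

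**Inputs.** Part 1 is Days 1–30, the first Part 2 dose is Day 31 and the latest planned dose is Day 90 (SAP 4.4). The Part 2 TEAE window is then Days 31–119 (90 + 29), or 89 days. The Part 1 window ends on Day 59 (30 + 29). Assumed: all 365 start dates in 2018, with every onset day equally likely.

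**How often the months coincide.** They differ only when Day 31 is the 1st of a month, which is 12 start dates. The shared-month rule governs the other 353/365 = 97%.

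**Day missing.**
- If the first Part 2 dose is on day d of a 30-day month, (31 − d)/30 of that month's days are open-label. Over d = 2 to 30 the mean is 15/30 = 50%; d = 3 gives 28/30 = 93%. All are dated to the 1st.
- Over all start dates, 5,373 open-label onset days are lost (14.72 per start date × 365). The 12 exempt start dates keep 365. The loss within the transition month is 5,373/(5,373 + 365) = 94%.
- Per subject this is 14.72/89 = 16.5% of the Part 2 window, or 14.72/60 = 24.5% of Part 2 dosing days. Moving the Day 31 visit by −2 or +2 days gives 16.2% to 16.9% of the window.

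**Year only.** About 80% of onset days in the Part 2 window go to the first Part 1 dose. About 8% match no rule, because Part 1 straddles the new year.

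**Undated, not flagged pre-treatment.** All go to the first Part 1 dose, although 60/90 = 67% of a completer's planned dosing days are in Part 2.

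**Example.** First dose 4 May 2018, last Part 1 dose 2 June, first Part 2 dose 3 June. The Part 1 window ends on 1 July.

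| True onset | Recorded as | TEAE if fully dated | Imputed date | TEAE after imputation |
|---|---|---|---|---|
| 25 June | June 2018 | Parts 1 and 2 | 1 June | Part 1 only |
| 15 July | nothing | Part 2 only (43 + 1 = 44 > 30) | 4 May | Part 1 only |

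The first row loses Part 2 status but leaves Part 1 as it was. The second also adds a Part 1 event.

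**Size per subject.** If all 20 enter Part 2, one subject lost from the numerator moves the Part 2 overall figure by 1/20 = 5 points, the TAK-935-first column by 1/16 = 6.25 points and the placebo-first column by 1/4 = 25 points.

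**The case against.** Three stronger readings are tempting, and the documents do not support them.

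- **That the transition-month rule credits open-label events to placebo and so moves the four-subject Part 1 placebo column by 25 points.** A fully dated onset on Days 31–59 is already a Part 1 TEAE, because that window is not cut at the first Part 2 dose. Every later day of a shared month lies inside it, except the 31st when the last Part 1 dose was on the 1st. Imputation adds placebo credit essentially only for year-only or undated events that truly began after Day 59, and a 25-point shift would need the event to be that subject's only Part 1 TEAE.
- **That the rules favour TAK-935.** For the planned 16 subjects on TAK-935 in Part 1, a doubtful event goes to the TAK-935 column of the controlled part, which counts against the drug.
- **That the two transition-month rules contradict each other.** When the doses fall in different months, the recorded month already lies wholly after the last Part 1 dose, so there is little doubt to resolve.

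It can also fairly be said that start and stop dates and times are requested for every AE (Protocol 10.2.1.2), that missing and inconsistent entries are queried (Protocol 12.1), and that a blinded data review precedes lock (Protocol 13.1). The combined Part 1 and 2 summary keeps these events, though under the Part 1 treatment column. No inference is planned on TEAEs. On average about half the days in a shared month really are Part 1 days.

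These points make the problem small. They do not restore the event to the Part 2 table, which has its own primary endpoint.

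**Conclusion.** The concern holds in a limited form. For subjects who enter Part 2, the start-date rules remove transition-month, most year-only and all undated AEs (not flagged pre-treatment) from the Part 2 TEAE count, even when onset was on open-label TAK-935. The direction is systematic: the Part 2 percentage can be understated by these rules.

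The likely size is small. The documents give no rate of incomplete dates, so the number of affected events is unknown and probably low. Because the endpoint is per subject, the percentage changes only for someone with no other Part 2 TEAE. The proportions above assume the planned dosing days and equally likely onset days. This is an inexpensive improvement to the Part 2 analysis; the Part 1 placebo comparison is largely untouched.

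**What to change.** For every subject who entered Part 2, whichever Part 1 arm, impute an ambiguous AE start date to the first Part 2 dose date when that date is compatible with the recorded parts. Do not do so if the AE is flagged pre-treatment, or if its recorded parts, end date or visit of report show that it began before that dose; the current rules then apply. Cover the year-only case that now matches no rule. Keep the current rules for subjects who never entered Part 2.

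The imputed event then counts in Part 2. It also still counts in Part 1, because with a Day 30 last dose 31 − 30 + 1 = 2 ≤ 30. The SAP should either accept and state that double count, or end the Part 1 TEAE window at the first Part 2 dose for continuing subjects. The second option is needed if open-label events are not to be credited to placebo. Flag imputed AEs in the listings.

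The cost is SAP wording and imputation code. Some true Part 1 events with incomplete dates will be counted in Part 2, and if the Part 1 window is also cut they will leave the Part 1 table.
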